## 6.6.4 Guidelines for Dose Modification Due to Adverse Events

### 6.6.4.1 Dose Modification for MK-8353 and Selumetinib

Adverse events (both nonserious and serious) associated with MK-8353 and selumetinib exposure may occur shortly after the first dose or several months after the last dose of treatment.

The CTCAE v4.0 must be used to grade the severity of AEs for individual participants. The investigator may attribute each toxicity event to MK-8353 alone, to selumetinib alone, or to the combination, but modification of the doses of both drugs must be followed according to [Table 7](#). Examples of dose reduction are as follows:

#### Example 1:

If a participant is receiving a dose along the MTD① diagonal of the dose combination grid (eg, Dose Level 5, which is MK-8353 200 mg and selumetinib 100 mg) and per [Table 7](#) a dose reduction is indicated, both MK-8353 and selumetinib will have doses reduced to the next lower dose level along the diagonal (eg, to Dose Level 3, which is MK-8353 150 mg and selumetinib 75 mg).

Example 2:

If a participant is receiving a dose along one of the off-diagonal dose sequences and per [Table 7](#) a dose reduction is indicated, both MK-8353 and selumetinib will have doses reduced along the diagonal of the dose combination grid to the next lower dose level sequentially, as shown in [Figure 4](#).

[figure not shown]

Figure 4 Example of Sequential Dose Reduction Along the Off-Diagonal Sequences

ERK = extracellular signal-regulated kinase;  
 MEK = mitogen-activated protein/extracellular signal regulated kinase

Example 3:

If a participant is receiving a dose combination where one of the drugs (MK-8353 or selumetinib) is already at their lowest dose level (eg, MK-8353 50 mg or selumetinib 25 mg) and per [Table 7](#) a dose reduction is indicated, then participants should be discontinued. [Table 6](#) provides some examples of what the dose reductions would be for various dose levels.

Table 6 Examples of Maximum Dose Reductions

Selumetinib/MK-8353	Selumetinib/MK-8353 1 st dose reduction	Selumetinib/MK-8353 2 nd dose reduction
75 mg /250 mg	50 mg/200 mg	25 mg/150 mg
50 mg /250 mg	25 mg/200 mg	off study
75 mg /200 mg	50 mg/150 mg	25 mg/100 mg
50 mg /200 mg	25 mg/150 mg	off study
50 mg /150 mg	25 mg/100 mg	off study
125 mg /150 mg	100 mg/100 mg	75 mg/50 mg
100 mg /150 mg	75 mg/100 mg	50 mg/50 mg
125 mg /100 mg	100 mg/50 mg	off study
100 mg /100 mg	75 mg/50 mg	off study
75 mg /100 mg	50 mg/50 mg	off study

If a dose modification for toxicity occurs with MK-8353 or selumetinib, the dose may not be re-escalated to the dose that preceded the dose modification. Dose modifications will be based on the previous cycle.

Participants may have up to 2 dose modifications of MK-8353 and selumetinib throughout the course of the study, as described in [Table 7](#). If further toxicity occurs or the criteria for resuming treatment are not met, the participant must be discontinued from the study treatment. If a participant experiences several toxicities and there are conflicting recommendations, follow the most conservative dose adjustment recommended (dose reduction appropriate to the most severe toxicity).

Exceptional circumstances to following the dose modification tables below may be considered after consultation with the Sponsor.

Table 7 MK-8353 and Selumetinib Dose Modification and Treatment Discontinuation Guidelines for Drug-Related Adverse Events

Eye disorders – Retinal Events (including serous detachment of the retina)	
Grade 1	Maintain dose level of MK-8353 and selumetinib and repeat ophthalmic monitoring including visual acuity assessment and ocular coherence tomography (OCT) within 10 days.
Grade 2	Interrupt MK-8353 and selumetinib dosing and refer the participant to ophthalmologist within 1 week and obtain OCT within 10 days: If resolved to baseline or Grade $\leq 1$ within 10 days, resume treatment at current dose level and continue schedule of visual assessments established per protocol. If not resolved to baseline or Grade $\leq 1$ within 10 days, resume treatment at reduced dose level and continue the schedule of events of visual assessments established per protocol.
Grade 3	Interrupt MK-8353 and selumetinib and refer the participant to ophthalmologist within 1 week and obtain OCT: If resolved to baseline or Grade $\leq 1$ within 7 days, resume treatment at a reduced dose level and continue schedule of visual assessments established per protocol. If not resolved to baseline or Grade $\leq 1$ within 7 days, continue to hold the MK-8353 and selumetinib dose and repeat ophthalmic assessment in 10 days. If resolved to baseline or Grade $\leq 1$ , resume treatment at reduced dose level and continue schedule of visual assessments established per protocol. If remains Grade 3, permanently discontinue MK-8353 and selumetinib.
Grade 4	Permanently discontinue MK-8353 and selumetinib and immediately follow up with ophthalmic monitoring.
Eye disorder – Retinal Vein Occlusion (RVO)	
Any Grade	Permanently discontinue MK-8353 and selumetinib.
Other Eye Disorders (ie, Non-retinal Events)	
Grade 1-2	Maintain dose level of MK-8353 and selumetinib and increase frequency of ophthalmic monitoring to at least 14 days until stabilization or resolution.
Grade 3	Interrupt MK-8353 and selumetinib and refer participant to ophthalmologist within 1 week: If resolved to Grade $\leq 1$ in $\leq 21$ days, reduce 1 dose level of MK-8353 and selumetinib. If not resolved to Grade $\leq 1$ in $\leq 21$ days, permanently discontinue MK-8353 and selumetinib.
Grade 4	Permanently discontinue MK-8353 and selumetinib.

Liver-related Adverse Events	
Grade 1 AST or ALT (> ULN - 3 × ULN)	Maintain dose level of MK-8353 and selumetinib.
Grade 2 AST or ALT (>3 - 5.0 × ULN) or 3 × baseline value (if liver metastasis) AND blood bilirubin ≤2.0 × ULN	Interrupt dose of MK-8353 and selumetinib until resolved to Grade ≤1 (or Grade ≤2 in case of liver metastasis), then: 
 
• If resolved in ≤14 days, maintain dose level of MK-8353 and selumetinib.
 
• If resolved in >14 days, reduce dose level of MK-8353 and selumetinib.
 
 Recurrence: 
 
• Interrupt dosing of MK-8353 and selumetinib until resolved to Grade ≤1 (or Grade ≤2 in case of liver metastasis), then resume treatment at a reduced dose.
 

Grade 2 AST or ALT (> 3 - 5.0 × ULN) or 3 × baseline value (if liver metastasis) AND blood bilirubin > 2.0 × ULN	Interrupt dose of MK-8353 and selumetinib until resolved to Grade ≤1 (or Grade ≤2 in case of liver metastasis), then: 
 
• If resolved in ≤7 days, resume treatment at a reduced dose of MK-8353 and selumetinib.
 
• If not resolved in ≤7 days, permanently discontinue MK-8353 and selumetinib.
 

Grade 3 AST or ALT (>5.0 - 8.0 × ULN) AND blood bilirubin ≤2.0 × ULN	Interrupt dose of MK-8353 and selumetinib until resolved to Grade ≤1 (or Grade ≤2 in case of liver metastasis), then: 
 
• If resolved in ≤14 days, maintain dose level of MK-8353 and selumetinib.
 
• If resolved in >14 days, reduce dose level of MK-8353 and selumetinib.
 
 Recurrence: 
 
• Interrupt dosing of MK-8353 and selumetinib until resolved to Grade ≤1 (or Grade ≤2 in case of liver metastasis), then resume treatment at a reduced dose.
 

AST or ALT (>8 x ULN) AND blood bilirubin* ≤ 2.0 × ULN	Permanently discontinue MK-8353 and selumetinib.
AST or ALT (>5.0 × ULN) AND blood bilirubin* >2.0 × ULN	Permanently discontinue MK-8353 and selumetinib.
AST or ALT Grade 4 (>20.0 × ULN)	Permanently discontinue MK-8353 and selumetinib.

Cardiac Disorders	
Left ventricular systolic dysfunction Asymptomatic decrease of >10% in LVEF compared to baseline and the LVEF is below the institution's lower limit of normal	
Interrupt dose of MK-8353 and selumetinib and repeat evaluation of LVEF within 2 weeks.
 
 
If the LVEF recovers (defined as LVEF <math>\geq 50\%</math> or <math>\geq</math>LLN and absolute decrease <math>\leq 10\%</math> compared to baseline) <math>\leq 3</math> weeks, reduce 1 dose level after approval of the Sponsor Medical Monitor. Monitor LVEF 2 weeks after restarting on MK-8353 and selumetinib, every 4 weeks for 12 weeks and subsequently as per protocol.
 
If the LVEF does not recover within 3 weeks, permanently discontinue participant from study treatment. Closely monitor LVEF until resolution (or 16 weeks).
 

Grade 3-4	Permanently discontinue participant from MK-8353 and selumetinib. Closely monitor LVEF until resolution (or 16 weeks).
CK Elevation	
Grade 1-2	
Continue treatment on same dose level. Ensure patient is adequately hydrated. Monitor closely CK and serum creatinine levels.                      (If total CK <math>\geq 3 \times</math> ULN, measure isoenzymes and myoglobin in blood and urine).

Grade 3 (>5.0 - 10.0 $\times$ ULN) without renal impairment (ie, serum creatinine $< 1.5 \times$ ULN or $1.5 \times$ baseline)	
If asymptomatic, maintain dose of MK-8353 and selumetinib. Monitor closely and measure isoenzymes and myoglobin in blood and urine.
 
If symptomatic (muscle pain/spasms or muscle weakness), interrupt dose of MK-8353 and selumetinib until resolved to CTCAE Grade <math>\leq 1</math> and monitor closely, then:
 
 
If resolved in <math>\leq 21</math> days, reduce 1 dose level of MK-8353 and selumetinib.
 
If resolved in <math>> 21</math> days, permanently discontinue MK-8353 and selumetinib.
 

Grade 4 without renal impairment (ie, serum creatinine $< 1.5 \times$ ULN or $1.5 \times$ baseline)	
If asymptomatic, interrupt dose of MK-8353 and selumetinib and monitor closely. Ensure patient is adequately hydrated and monitor and measure isoenzymes and myoglobin in blood or urine, and serum creatinine.
 
 
If resolved in <math>\leq 21</math> days, reduce 1 dose level of MK-8353 and selumetinib.
 
If resolved in <math>> 21</math> days, permanently discontinue MK-8353 and selumetinib.
 
If symptomatic, permanently discontinue MK-8353 and selumetinib.
 
 
If symptomatic (muscle pain/spasms), permanently discontinue MK-8353 and selumetinib.

Grade 3 or 4 with renal impairment (ie, serum creatinine $\geq 1.5 \times$ ULN or $1.5 \times$ baseline)	
Interrupt MK-8353 and selumetinib dose until resolved to Grade <math>< 1</math> or baseline level. Ensure patient is adequately hydrated. Monitor isoenzymes and myoglobin in blood or urine, and serum creatinine, then:
 
 
If resolved in <math>\leq 21</math> days, reduce 1 dose level of MK-8353 and selumetinib.
 
If resolved in <math>> 21</math> days, permanently discontinue MK-8353 and selumetinib.
 
 
Recurrence:
 
 
Permanently discontinue MK-8353 and selumetinib
 

Rash	
Grade 1	Treatment with MK-8353 and selumetinib should be maintained at the current dose. Initiate prophylactic regimen if it was not already and monitor closely.
Grade 2	First occurrence: Treatment with MK-8353 and selumetinib should be maintained at the current dose and rash should be closely monitored. Initiate prophylactic regimen if it was not already started. Reassess within a maximum of two weeks. If rash worsens or does not improve, interrupt dosing until improvement to Grade $\leq 1$ . Resume treatment at the same dose level.  Second occurrence: Reassess within a maximum of 2 weeks. If rash worsens or does not improve, interrupt dosing until improvement to Grade $\leq 1$ . Resume treatment at a reduced dose level. Only one dose reduction is permitted.
Grade 3	First occurrence: Treatment with MK-8353 and selumetinib should be interrupted. Reassess the participant weekly. Consider referral to dermatologist and manage rash per dermatologist's recommendation. Interrupt treatment until improvement to Grade $\leq 1$ . Resume treatment with MK-8353 and selumetinib at a reduced dose level.  Second occurrence: Interrupt treatment until improvement to Grade $\leq 1$ . Resume treatment with MK-8353 and selumetinib at a reduced dose level. If participant is at the lowest dose, participant should be discontinued. Consider referral to dermatologist and manage rash per dermatologist's recommendation.
Grade 4	Permanently discontinue MK-8353 and selumetinib.
Diarrhea	
Uncomplicated Grade 1-2	Consider temporary interruption of MK-8353 and selumetinib until resolved to Grade $\leq 1$ . Treatment with MK-8353 and selumetinib may then be resumed at the same dose level.
Complicated Grade 1-2	Temporarily interrupt MK-8353 and selumetinib treatment until resolved to Grade $\leq 1$ . Restart MK-8353 and selumetinib at one reduced dose level. If participant is at the lowest dose, participant should be discontinued.
Grade 3-4	Temporarily interrupt MK-8353 and selumetinib treatment until resolved to Grade $\leq 1$ . Restart MK-8353 and selumetinib at a reduced dose level. If participant is at the lowest dose, participant should be discontinued.
Nausea/Vomiting	
Grade 1-2	Treatment with MK-8353 and selumetinib should be maintained at the current dose. Promptly institute antiemetic measure.
Grade 3	Temporarily interrupt MK-8353 and selumetinib treatment until resolved to Grade $\leq 1$ . Resume treatment with MK-8353 and selumetinib at the same dose if, in the judgment of the investigator, the toxicity is considered to be unrelated to selumetinib, or at one reduced dose level.  Note: Interrupt dose for $\geq$ Grade 3 vomiting or Grade 3 nausea only if the vomiting or nausea cannot be controlled with optimal antiemetics (as per local practice).
Grade 4	Permanently discontinue MK-8353 and selumetinib treatment

Interstitial Lung Disease/Pneumonitis	
Grade 1	Maintain dose level of MK-8353 and selumetinib. Monitor weekly.
Grade 2	Withhold MK-8353 and selumetinib for up to 3 weeks. 
 
• If improved to Grade 0 or 1, resume treatment at 1 reduced dose level of MK-8353 and selumetinib
 
• If not resolved within 3 weeks, permanently discontinue MK-8353 and selumetinib.
 

Grade 3-4	Permanently discontinue MK-8353 and selumetinib.
Venous Thromboembolism	
Uncomplicated DVT or PE	Withhold MK-8353 and selumetinib for up to 3 weeks. 
 
• If improved to Grade 0 or 1, resume at reduced dose.
 
• If not improved, permanently discontinue.
 

Life threatening PE	Permanently discontinue MK-8353 and selumetinib.
All other Adverse Events (suspected to be related)	
Grade 1-2	If the event is a persistent Grade 2 AE not responsive to a specific therapy, consider MK-8353 and selumetinib interruption or reduction.
Grade 3	For other AEs, interrupt MK-8353 and selumetinib until resolution to Grade $\leq$ 1 or to pre-treatment/baseline level. If the event resolves within 21 days, then MK-8353 and selumetinib may be restarted at a lower dose (one level below that previously received) based upon the Investigator's discretion.
Grade 4	Permanently discontinue study drug (MK-8353 and selumetinib).

AE = adverse event; ALT = alanine aminotransferase; AST = aspartate aminotransferase; CK = creatine kinase; CTCAE = Common Terminology Criteria for Adverse Events; LLN = lower limit of normal; LVEF = left ventricular ejection fraction; ULN = upper limit of normal

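### Table 7, Grade 2 AST/ALT with bilirubin above 2 × ULN: with liver metastases the restart test is already met at onset for values up to 5 × ULN, and no bilirubin recovery level is given

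*Combined protocol and SAP*

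**What the plan says.** The liver block of Table 7 (Section 6.6.4.1) has two rows for Grade 2 AST/ALT. Both are entered at more than 3 and up to 5.0 × ULN, or at three times baseline with liver metastases. They differ in bilirubin.

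- **Bilirubin above 2.0 × ULN.** The entry condition ends "3 × baseline value (if liver metastasis) AND blood bilirubin > 2.0 × ULN". The action is "Interrupt dose of MK-8353 and selumetinib until resolved to Grade ≤1 (or Grade ≤2 in case of liver metastasis), then" one of two branches. If the event resolves within 7 days, treatment resumes at a reduced dose. The other branch is "If not resolved in ≤7 days, permanently discontinue MK-8353 and selumetinib". Bilirubin is not mentioned in the action cell.
- **Bilirubin at or below 2.0 × ULN.** The restart test is the same. The early branch is "If resolved in ≤14 days, maintain dose level of MK-8353 and selumetinib".

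Just above this range, the row "AST or ALT (>5.0 × ULN) AND blood bilirubin* >2.0 × ULN" leads to permanent discontinuation. The footnote to its asterisk is not in the text available here, so how that row applies is taken at face value.

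Table 3 (Section 5.1) admits participants with liver metastases at AST/ALT up to 5 × ULN.

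**The concern.** A rule that interrupts dosing until a test is passed needs a test that the participant fails when the interruption starts. In the row with bilirubin above 2 × ULN, a participant with liver metastases at, say, 4.5 × ULN passes at once. Bilirubin is what separates this row from its neighbour: it shortens the window from 14 to 7 days and adds a permanent stop. Yet it appears only as a condition for entering the row.

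A site that applies the AST/ALT wording as written could re-dose a participant who has combined AST/ALT and bilirubin elevation, without any fall in either. Section 8.4.7 treats that pattern, when alkaline phosphatase is below 2 × ULN, as needing further evaluation of its cause. What is at stake is the safety of a limited group, and consistent handling of the same event across sites.

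**Working it through.** The plan states no figure on this point. The check sets the row's entry condition against its exit condition.

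**Inputs.** Table 7: Grade 1 is above 1 and up to 3 × ULN, Grade 2 above 3 and up to 5 × ULN, and Grade 3 starts above 5 × ULN. Restart test with liver metastases: Grade 2 or lower. Table 3: baseline AST/ALT up to 5 × ULN with liver metastases. Schedule: twice daily, 4 days on and 3 off, in 3-week cycles.

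**Step 1: entry by the ULN range.** A value above 3 and up to 5 × ULN is Grade 2 throughout. Grade 2 or lower is therefore met on day 0 for every such event with liver metastases.

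**Step 2: entry by three times baseline only.** The row could instead mean that this is the only trigger for participants with liver metastases. With baseline b (in × ULN), the trigger value is 3b.

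- 3 < 3b ≤ 5 gives 3/3 < b ≤ 5/3, so b is above 1.0 and up to 1.67. The test is met on day 0. Example: b = 1.5 gives 4.5 × ULN, Grade 2.
- b above 1.67 gives 3b above 5. Example: b = 2 gives 6 × ULN. With bilirubin above 2 × ULN, the permanent-stop row appears to apply. At the entry limit, b = 5 gives 15 × ULN, with the same result.

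On either reading, the gap lies at or below 5 × ULN.

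**Step 3: the two branches.** Because the AST/ALT test is met on day 0, the 7-day resume branch applies immediately and the permanent-stop branch cannot be reached while AST/ALT stays at or below 5 × ULN. Without liver metastases, the same event must fall to 3 × ULN or below within 7 days or treatment stops.

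**Step 4: does another provision set a bilirubin restart level?**

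- DLT criterion 6 (Section 6.6.2): classifies related Cycle 1 events with alkaline phosphatase below 2 × ULN as DLTs; no restart level. After a DLT, continuing requires Sponsor discussion (Section 5.6).
- ECI rule (Section 8.4.7) and Table 9 (Section 8.4.1): evaluation, site guidance held in the study binder, and reporting of potential drug-induced liver injury within 24 hours. The ECI rule has the same alkaline phosphatase condition. No restart level is stated in the protocol.
- Section 7.1: discontinuation where the investigator or Sponsor sees unnecessary risk; a judgment, not a level.
- Section 8.3.7: repeat testing of clinically significant values; not a dosing rule.
- Table 7, all other adverse events: if bilirubin is itself recorded as a related Grade 3 event, dosing is held until Grade 1 or lower "or to pre-treatment/baseline level", and the instruction to "follow the most conservative dose adjustment recommended" would bring that in. At Grade 1-2 the row says only: "If the event is a persistent Grade 2 AE not responsive to a specific therapy, consider MK-8353 and selumetinib interruption or reduction".

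Only the Grade 3 route sets a level.

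**Step 5: doses.** Cycle 1 has 3 × 4 × 2 = 24 doses of each drug. Immediate restart misses 0. A hold covering one 4-day block misses 8/24 = 33.3%. Six missed doses are 6/24 = 25.0%, which is not above 25%; seven are 7/24 = 29.2%, which is.

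**The case against.** The strongest reply is that the row describes a joint event. While bilirubin stays above 2 × ULN and AST/ALT is unchanged, the participant still fits the row that orders interruption. A zero-length hold would empty both that order and the 7-day branch, so resolution must be meant to cover bilirubin. This is a reasonable reading, and it prevents the claim that the row fails on every reading. It does not settle what bilirubin must fall to: 2 × ULN, the normal limit, Grade 1 or baseline are all open, and sites could differ.

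The second reply is that the safeguards make unsafe re-dosing unlikely. They do reduce the risk: restart is only at a reduced dose, a participant already at the lowest dose of either drug is discontinued (Section 6.6.4.1, Example 3), the Sponsor hears of potential liver injury within 24 hours, and the investigator can stop treatment. A reader might infer that the plan leaves combined liver signals unmanaged; the documents do not support that. The remaining gap is widest after Cycle 1 or when alkaline phosphatase is 2 × ULN or more, because criterion 6 then does not apply.

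A reader might also infer that the row with bilirubin at or below 2 × ULN is faulty, since its test is met at onset in the same way. The documents do not support that either. Dosing at Grade 2 or lower with low bilirubin matches the 5 × ULN entry limit. Tightening it would hold a Grade 2 event to a stricter restart test than the Grade 3 row, where the hold works because AST/ALT must fall from above 5 to 5 × ULN or below. It could also create extra Cycle 1 DLTs under criterion 9 that feed the mTPI decisions. No change is claimed there.

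**Conclusion.** The concern holds for one row and one group: participants with liver metastases, AST/ALT at or below 5 × ULN, and bilirubin above 2.0 × ULN. For them, on the row's stated criterion, neither the hold nor the 7-day stop has any effect, and a reduced-dose restart is open while bilirubin remains raised. This is more than missing detail, because a stated safety rule does not operate as written. Severity is low to moderate.

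The conclusion rests on three assumptions: that resolution refers to the AST/ALT grade, the only criterion the row names; that AST/ALT is graded by Table 7's own bands; and that the permanent-stop row covers values above 5 × ULN, subject to the footnote that is not available. Site guidance in the study binder could not be seen and might supply a level. No fault is claimed for participants without liver metastases or in the Grade 3 row.

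**What to change.** In the Grade 2 row with bilirubin above 2.0 × ULN only, add a second restart condition. Treatment resumes at the reduced dose if, within 7 days, the existing AST/ALT criterion is met and bilirubin is at or below 2.0 × ULN or the participant's baseline. Otherwise, discontinue permanently. The baseline alternative is needed because Table 3 admits total bilirubin above 1.5 × ULN when direct bilirubin is below ULN. A participant whose bilirubin has not risen from a baseline above 2 × ULN would then still have no hold to serve, which seems acceptable.

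The change is one reworded row in an amendment, with no scheduled visits added. Its price is some longer holds or permanent stops, including for participants without liver metastases who enter this row. In Cycle 1, a drug-related hold that misses one 4-day block (8 of 24 doses, 33.3%) is a DLT under criterion 9 and also exceeds the 25% missed-dose limit in Section 7.1. The added DLTs should be few, because related Cycle 1 events with alkaline phosphatase below 2 × ULN are already DLTs under criterion 6. Up to 6 missed doses (25.0%) crosses neither limit, so prompt repeat testing would contain the cost; Section 8.3.7 asks for repeats but sets no timing. Section 7.1 does not state its denominator. If doses are counted from Day 1, one block missed in Cycle 2 is 8/48 = 16.7% at the end of that cycle, below the limit.

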(Note: This criterion is not applicable if: (1) the initial AE resulted in death or permanent disability, or (2) the study is a single-dose drug study; or (3) Sponsor's product(s) is/are used only 1 time.)

NOTE: IF A RECHALLENGE IS PLANNED FOR AN AE THAT WAS SERIOUS AND MAY HAVE BEEN CAUSED BY THE SPONSOR'S PRODUCT, OR IF RE-EXPOSURE TO THE SPONSOR'S PRODUCT POSES ADDITIONAL POTENTIAL SIGNIFICANT RISK TO THE PARTICIPANT THEN THE RECHALLENGE MUST BE APPROVED IN ADVANCE BY THE SPONSOR CLINICAL DIRECTOR AS PER DOSE MODIFICATION GUIDELINES IN THE PROTOCOL, AND IF REQUIRED, THE INIRB/IEC.

- **Consistency with study intervention profile:** Is the clinical/pathological presentation of the AE consistent with previous knowledge regarding the Sponsor's product or drug class pharmacology or toxicology?
- The assessment of relationship will be reported on the case report forms/worksheets by an investigator who is a qualified physician according to his/her best clinical judgment, including consideration of the above elements.
- Use the following scale of criteria as guidance (not all criteria must be present to be indicative of a Sponsor's product relationship).
  - Yes, there is a reasonable possibility of Sponsor's product relationship:
    - There is evidence of exposure to the Sponsor's product. The temporal sequence of the AE onset relative to the administration of the Sponsor's product is reasonable. The AE is more likely explained by the Sponsor's product than by another cause.
  - No, there is not a reasonable possibility of Sponsor's product relationship:
    - Participant did not receive the Sponsor's product OR temporal sequence of the AE onset relative to administration of the Sponsor's product is not reasonable OR the AE is more likely explained by another cause than the Sponsor's product. (Also entered for a participant with overdose without an associated AE.)
- For each AE/SAE, the investigator must document in the medical notes that he/she has reviewed the AE/SAE and has provided an assessment of causality.

- There may be situations in which an SAE has occurred and the investigator has minimal information to include in the initial report to the Sponsor. However, it is very important that the investigator always make an assessment of causality for every event before the initial transmission of the SAE data to the Sponsor.

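### Table 7 permanently stops symptomatic Grade 4 CK elevation without renal impairment, but allows a restart when renal impairment is present

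*Combined protocol and SAP*

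**What the plan says.** Section 6.6.4.1, Table 7, has three CK rows above Grade 2.

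- **Grade 3 without renal impairment.** For a participant without symptoms: "If asymptomatic, maintain dose of MK-8353 and selumetinib". With symptoms, both drugs are held; they restart one level lower if the event resolves within 21 days and stop for good otherwise.
- **Grade 4 without renal impairment.** Without symptoms, the same hold, 21-day limit and one-level reduction apply. With symptoms: "If symptomatic (muscle pain/spasms), permanently discontinue MK-8353 and selumetinib". The cell states this stop twice.
- **"Grade 3 or 4 with renal impairment".** There is no split by symptoms. The action is "Interrupt MK-8353 and selumetinib dose until resolved to Grade" below 1, or baseline. Treatment then restarts one level lower if this takes 21 days or less, and stops permanently if it takes longer or the event recurs.

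Renal impairment is defined inside these headings by creatinine at 1.5 × ULN or 1.5 × baseline.

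Section 7.1 adds a separate rule. A participant comes off treatment after a toxicity-related interruption of more than 14 consecutive days in Cycle 1, or with more than 25% of doses missed cumulatively.

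**The concern.** A participant with symptomatic Grade 4 CK elevation and normal creatinine must stop. The same participant with raised creatinine may, on the text, be dosed again after recovery. The second presentation is the more serious one, so the rule points the wrong way for that cell. The cause appears to be that Grades 3 and 4 were merged in the renal row and the symptom branch was lost. What is at stake is re-exposure to both drugs after a severe muscle event, in a table that sites are expected to follow as written.

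**Working it through.** The plan gives no figure to reproduce. The check is a comparison of rows, followed by three short calculations.

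**1. The four CK cells (Table 7)**

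| Grade and symptoms | Without renal impairment | With renal impairment | Renal row is |
|---|---|---|---|
| 3, asymptomatic | maintain dose | hold, then reduce | stricter |
| 3, symptomatic | hold, then reduce | hold, then reduce; stop on recurrence | stricter |
| 4, asymptomatic | hold, then reduce | hold, then reduce; stop on recurrence | stricter |
| 4, symptomatic | permanent stop | hold, then reduce; stop on recurrence | less strict |

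One cell of four is reversed. For context, 11 rows of Table 7 name Grade 4. Eight stop permanently: retinal, other eye, AST/ALT, cardiac, rash, nausea/vomiting, interstitial lung disease, and all other events. Three allow a restart: the two CK rows and diarrhea. Of the two CK rows, only the renal one allows a restart with symptoms.

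**2. How much Section 7.1 closes**

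Dosing is twice daily, 4 days on and 3 days off, in a 3-week cycle (Sections 1.3 and 6.6.3.1). Doses per cycle = 4 × 3 × 2 = 24. Since 25% of 24 is 6, the limit is passed at 7 missed doses.

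- A full one-week hold misses 4 × 2 = 8 doses, and 8/24 = 33%. In Cycle 1 this forces discontinuation.
- With onset in the first two weeks of Cycle 1, the longest hold that stays at 6 missed doses is about 6 calendar days. For example, a hold over Days 2 to 7 misses Days 2, 3 and 4, which is 6/24 = 25% and not above the limit.
- With onset on Day 16 or later, only Days 16 to 18 remain, so at most 3 × 2 = 6 doses can be missed in Cycle 1. The 25% limit cannot be reached in that cycle.
- In later cycles the text does not say whether the 25% limit applies. If it covers Cycle 1 only, Section 7.1 sets no such limit there. If it is counted over all doses to date, a one-week hold in Cycle 2 gives 8/48 = 17% at the end of that cycle and does not trigger it. If it applies to each cycle separately, the same hold gives 33% and does.

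**3. Do the two headings exclude each other?**

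Let b be baseline creatinine and c on-treatment creatinine, both divided by ULN. Read literally, the row without impairment is met if c < 1.5 or c < 1.5b, and the row with impairment if c ≥ 1.5 or c ≥ 1.5b. Both are met when c lies between 1.5b and 1.5.

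- b = 0.6: 1.5b = 0.9, so 0.9 ≤ c < 1.5 meets both.
- b = 1.2: 1.5b = 1.8, so 1.5 ≤ c < 1.8 meets both.
- b = 1.0: no overlap.

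A participant going from 0.6 to 0.9 × ULN with symptomatic Grade 4 CK therefore meets one row that says stop and one that allows a restart.

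**4. Could the study drug itself move someone into the renal row?**

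Section 2.2.3.1 says MK-8353 inhibits transporters that carry about 10% to 40% of creatinine clearance. Assume complete inhibition with filtration and creatinine production unchanged. Creatinine then rises by a factor 1/(1 − s), where s is the secreted share: 1/0.9 = 1.11 at 10% and 1/0.6 = 1.67 at 40%. The factor reaches 1.5 at s = 1/3. So at the upper end of the range, and only under that assumption, a transporter effect with no change in muscle injury could move a participant from the stop row to the restart row.

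**The case against.** The strongest reply is that other rules catch this participant.

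- **Section 7.1.** This stands in part. It removes most longer holds that begin early in Cycle 1, so Table 7's 21-day window is largely unavailable there. It does not reach the cases listed in step 2.
- **Rechallenge approval (Section 10.3.4).** For a serious event that may be drug-caused, "THE RECHALLENGE MUST BE APPROVED IN ADVANCE BY THE SPONSOR CLINICAL DIRECTOR AS PER DOSE MODIFICATION GUIDELINES IN THE PROTOCOL". This is a real check, and symptomatic Grade 4 CK with renal impairment could readily be serious. But the approval is tied to the dose modification guidelines, which send the decision back to the row in question.
- **Conflict rule.** "If a participant experiences several toxicities and there are conflicting recommendations, follow the most conservative dose adjustment recommended". It is worded for several toxicities. The CK row already builds creatinine into one toxicity and gives one instruction. If a creatinine rise were recorded separately at Grade 1 or 2, the row for other events would not require a permanent stop either.
- **Recording by diagnosis.** Section 10.3.4 asks for the diagnosis rather than its signs. If a site records one Grade 4 diagnosis, the row for all other events gives a permanent stop. This depends on how the site codes and grades the event; a diagnosis graded 3 could still restart.
- **Other caution in the renal row.** It sets a resolution target below Grade 1 or baseline, a dose reduction and a stop on recurrence, and the investigator may always discontinue. All true, but none of this makes the row as strict as a permanent stop.

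The gap is therefore narrower than Table 7 alone suggests, but it is not closed.

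**Conclusion.** The reversal is real and confined to one cell: symptomatic Grade 4 CK elevation with renal impairment. It remains open for short holds, for onset late in Cycle 1, and for later cycles if the 25% limit is read as Cycle 1 only. The documents give neither an incidence nor a usual time for CK to recover, so the number affected cannot be calculated. The cell needs Grade 4, symptoms and raised creatinine together, so it is likely to be small. No endpoint, sample size or escalation rule changes; in Cycle 1 the event would probably count as a DLT in any case (Section 6.6.2), though under Section 5.6 a DLT does not by itself end treatment.

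A reader might infer two stronger claims that the documents do not support. The first is that Table 7 is generally more lenient in renal impairment, or that these participants will routinely be re-dosed. Three of the four cells are stricter, and Section 7.1 ends treatment for many in early Cycle 1. The second is that the Grade 2 retinal line, which resumes at a reduced dose when the event has not resolved in 10 days, is a similar error. That line may mean late resolution or deliberate dosing at a lower level. Its row already requires ophthalmologist referral within 1 week and OCT within 10 days, and a lighter rule than for Grade 3 is ordinary grading.

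**What to change.** Make two edits to the CK section of Table 7.

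1. In the row for Grade 3 or 4 with renal impairment, add: *Grade 4 and symptomatic: permanently discontinue both drugs.*
2. Make the headings mutually exclusive. Without renal impairment: creatinine < 1.5 × ULN **and** < 1.5 × baseline. With renal impairment: creatinine ≥ 1.5 × ULN **or** ≥ 1.5 × baseline.

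The first edit removes the reversal. The second is needed as well, because the overlap also affects other cells. For example, asymptomatic Grade 3 CK with creatinine rising from 0.6 to 0.9 × ULN now meets both the instruction to maintain the dose and the instruction to hold it.

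The cost is one added line and two reworded headings. A few participants who might have restarted will stop, and those in the overlap will follow the renal row.
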